Diagnosis and Main Inclusion Criteria	
Inclusion criteria for patients:
 
 1. Age 60 and older 2. Meet criteria for either a) dementia with Lewy bodies, or b) Parkinson's disease dementia 3. Able to provide informed consent 4. Written and oral fluency in English 5. Able to participate in all scheduled evaluations and to complete all required tests and procedures. 6. In the opinion of the investigator, the subject must be considered likely to comply with the study protocol and to have a high probability of completing the study. 
Inclusion criteria for controls:
 
 1. Age 60 and older 2. Normal cognitive and motor function based on neurological examination 3. Written and oral fluency in English 4. Able to participate in all scheduled evaluations and to complete all required tests and procedures. 5. In the opinion of the investigator, the subject must be considered likely to comply with the study protocol and to have a high probability of completing the study. 
Exclusion criteria:
 
 1. Past or present history of certain brain disorders (other than DLB or PDD for patient participants). 2. Certain significant medical conditions, which make study procedures of the current study unsafe. Such serious medical conditions include uncontrolled epilepsy and multiple serious injuries. 3. Contraindication to MRI scanning 4. Conditions precluding entry into the scanners (e.g. morbid obesity, claustrophobia, etc.). 5. Exposure to research related radiation in the past year that, when combined with this study, would place subjects above the allowable limits. 6. Low affinity binding on TSPO genetic screen 7. Currently taking anticoagulant drugs (e.g., warfarin). 8. Women who are able to become pregnant.
Study Product, Dose, Route, Regimen	¹¹ C-PBR28, up to 20 mCi (740 MBq), IV, total of one injection.
Duration of administration	A single dose of radioligand will be injected over 1 minute for the PET scan.

CONFIDENTIAL

This material is the property of Columbia University Medical Center. Do not disclose or use except as authorized in writing by the study sponsor

Reference therapy	N/A

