PET imaging procedures. Subjects will undergo ^{11}C -PBR28 PET in the CUMC Kreitchman PET center on a Siemens Biograph mCT. Prior to PET imaging, one arterial catheter and one intravenous catheter will be placed. After a low-dose CT scan for attenuation correction, up to 20 mCi ^{11}C -PBR28 will be injected intravenously over 60 seconds. Emission scan will begin at the start of the radioligand infusion according to the following frame schedule: 30 seconds x 6, 1 minute x 3, 2 minutes x 2, and 5 minutes x 16 for total scan time of 90 min. During the emission scan, arterial samples will be drawn at 10 second intervals for the first 4 min using an automated blood sampler. Thereafter, manual arterial samples will be drawn at 6, 8, 10, 15, 20, 30, 40, 50, 60, 75, and 90 minutes. Radioactivity in plasma will be quantified by a γ -counter and analyzed by reverse-phase chromatography to separate parent radioligand from radiometabolites[43] by the PET center radiometabolite laboratory. Free fraction of ^{11}C -PBR28 in plasma (f_p) will be measured by ultrafiltration and normalized using a standard derived from pooled donor plasma[44].

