5.9.4 Return or Destruction of Study Drug

Any unused radiopharmaceutical will be on site and documented in the study files.

6 Study Procedures

This study will involve up to 3 outpatient visits. See schedule below.

At the first screening visit, subjects will sign informed consent, undergo history and physical and neurological examination, and have blood drawn for routine safety laboratories. Menopause (defined as absence of menses for at least one year) or history of hysterectomy and/or tubal ligation will be confirmed by medical history to exclude women of child-bearing potential. Blood will also be drawn for TSPO, ApoE and GBA genotyping if not previously performed in another study.

Brain MRI will take place at the Neurological Institute Neuro MRI Center on 3T Philips scanner. MRI will be performed to rule out intracranial disease other than PDD or DLB, and for coregistration with the PET images for analysis. An additional screening visit is required for brain MRI; however, this may be performed on the same day as the first screening visit is scheduling allows. Up to 2 screening visits are therefore anticipated. However, additional visits may be necessary if certain tests must be scheduled on different days due to scheduling. If subjects require a sedative for the MRI (e.g., because of claustrophobia), they may receive a onetime dose of lorazepam (0.5 - 1 mg orally) or equivalent dose of an alternative benzodiazepine prior to the MRI. Side effects of anti-anxiety medications may include prolonged sedation (usually less than 8 hours), lightheadedness, motor incoordination, difficulties with balance, or confusion. These effects are temporary and go away after several hours. Subjects will be instructed not to drive, handle machinery, or drink alcohol until the next day. Subjects who receive an anti-anxiety medication will be instructed to bring a companion to the MRI study

CONFIDENTIAL

This material is the property of Columbia University Medical Center. Do not disclose or use except as authorized in writing by the study sponsor

visit, and will be accompanied by a member of the study staff during the MRI. The PI will be available in the event of an adverse event during the MRI.

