One study visit will be required for the ^{11}C -PBR28 PET scan. At the PET scan visit, one IV catheter will be placed by a qualified clinician for purposes of radioligand injection. After performing an Allen test to ensure ulnar perfusion to the hand, a catheter will be placed in the radial artery by a qualified clinician. After a CT attenuation scan, up to 20 mCi ^{11}C -PBR28 will be injected via the IV. The emission scan will last 90 minutes, during which members of the study team will draw arterial blood samples.

^{11}C -PBR28 PET scans must be completed within 12 months of the brain MRI. Other screening procedures must be done within 60 days prior to the PET scan.

Study Procedures	Screen ^a	Study ^b
	Day -60 to 1	Visit 1
Informed consent	X	
Medical history	X	
Inclusion/exclusion criteria	X	X
Blood draw for genetic tests	X	
MRI	X	
^{11}C -PBR28 PET		X
Laboratory determinations	X	
Neurological examination	X	
Vital signs	X	
Height and weight	X	
Adverse events	X	X

CONFIDENTIAL

This material is the property of Columbia University Medical Center. Do not disclose or use except as authorized in writing by the study sponsor

7 Statistical Plan

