8.1 Definitions

Adverse Event

An *adverse event* (AE) is any symptom, sign, illness or experience that develops or worsens in severity during the course of the study. Intercurrent illnesses or injuries should be regarded as adverse events. Abnormal results of diagnostic procedures are considered to be adverse events if the abnormality:

- results in study withdrawal

CONFIDENTIAL

This material is the property of Columbia University Medical Center. Do not disclose or use except as authorized in writing by the study sponsor

- is associated with a serious adverse event
- is associated with clinical signs or symptoms
- leads to additional treatment or to further diagnostic tests
- is considered by the investigator to be of clinical significance

Event

Adverse events are classified as serious or non-serious. A ***serious adverse event*** is any AE that is:

- fatal
- life-threatening
- requires or prolongs hospital stay
- results in persistent or significant disability or incapacity
- an important medical event

Important medical events are those that may not be immediately life threatening, but are clearly of major clinical significance. They may jeopardize the subject, and may require intervention to prevent one of the other serious outcomes noted above. For example, drug overdose or abuse, a seizure that did not result in in-patient hospitalization, or intensive treatment of bronchospasm in an emergency department would typically be considered serious.

All adverse events that do not meet any of the criteria for serious should be regarded as ***non-serious adverse events***.

Adverse Event Reporting Period

The study period during which adverse events must be reported is normally defined as the period from the initiation of any study procedures to the end of the study treatment followup. For this study, the study drug follow-up is defined as 24 hours following the last administration of study drug.

Preexisting Condition

A preexisting condition is one that is present at the start of the study. A preexisting condition should be recorded as an adverse event if the frequency, intensity, or the character of the condition worsens during the study period.

General Physical Examination Findings

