8.2 Recording of Adverse Events

At each contact with the subject, the investigator must seek information on adverse events (AEs) by specific questioning and, as appropriate, by examination. Information on all adverse events should be recorded immediately in the source document, and also in the appropriate adverse event module of the case report form (CRF). All clearly related signs, symptoms, and abnormal diagnostic procedures results should be recorded in the source document, though should be grouped under one diagnosis.

All adverse events occurring during the study period must be recorded. The clinical course of each event should be followed until resolution, stabilization, or until it has been determined that the study treatment or participation is not the cause. Serious adverse events that are still ongoing

at the end of the study period must be followed up to determine the final outcome. Any serious adverse event that occurs after the study period and is considered to be possibly related to the study treatment or study participation should be recorded and reported immediately.

As per CUMC IRB's Policy, Unanticipated Problems will be defined as follows:

Unanticipated Problem (UP) is any incident, experience or outcome involving risk to subjects or others in any human subjects research that meets all of the following criteria:

- Unexpected (in terms of nature, severity or frequency) given (a) the research procedures that are described in the IRB-approval protocol and informed consent document and (b) the characteristics of the subject population being studied;
- Related or possibly related to participation in such research (i.e., there is a reasonable possibility that the incident, experience or outcome may have been caused by the procedures involved in such research); and
- Suggests that the research places subjects or others at a greater risk of harm (including physical, psychological, economic or social harm) than was previously known or recognized (HHS IRB Guidance, Section I).

The following AEs will be considered Unexpected Problems:

- A single occurrence of a serious, unexpected event that is uncommon and strongly associated with drug exposure
- A single occurrence, or a small number of occurrences, of a serious, unexpected event that is not commonly associated with drug exposure
- Multiple occurrences of an AE that, based on an aggregate analysis, are determined not to be isolated occurrences and involve risk to human subjects

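### The adverse-event reporting period runs to 24 hours after injection, but no contact is shown after the PET visit, so events starting after discharge are collected only by selective self-report

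*Combined protocol and SAP*

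**What the plan says.** Section 8.1 (Adverse Event Reporting Period) describes the period as normally "the period from the initiation of any study procedures to the end of the study treatment followup", and then fixes its end for this study: "the study drug follow-up is defined as 24 hours following the last administration of study drug". The Study Summary provides for one injection: "A single dose of radioligand will be injected over 1 minute for the PET scan". The clock therefore runs for 24 hours from that injection.

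Section 8.2 says how events are sought: "At each contact with the subject, the investigator must seek information on adverse events (AEs) by specific questioning". It also requires that all events in the study period be recorded, whatever their cause.

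Section 6 sets out the contacts: "This study will involve up to 3 outpatient visits". Up to two are for screening and one is for PET. The schedule table has two columns, Screen (Day -60 to 1) and Study Visit 1, with adverse events marked in both. No later column, visit or call appears. On the PET visit itself, Section 6 says: "The emission scan will last 90 minutes, during which members of the study team will draw arterial blood samples". It does not say how long the subject stays afterwards.

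Under the Post-study Adverse Event heading, Section 8.1 has the investigator follow unresolved events. It also has each subject told, at the last visit, to report later events that the subject or a personal physician believes may be related to taking part.

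**The concern.** The reporting period extends well beyond the last contact the plan shows. Active questioning is tied to contacts, so an event that begins after the subject leaves the PET centre, but within 24 hours of injection, is inside the period in which everything must be recorded and outside any occasion on which someone asks. The one remaining route is a report started by the subject, filtered by a belief that the event is related. That is narrower than the Section 8.2 requirement, which has no such filter.

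What is at stake is the adverse-event record. Each scanned subject has a radial arterial catheter, an intravenous line and an investigational radioligand. A problem first noticed at home, or an intercurrent illness that nobody links to the study, could go unrecorded. Feasibility of this procedure in DLBD is the first primary objective, and the pilot is meant to inform a larger application, so how subjects fare after they leave is useful information. The regional binding estimates, effect sizes, coefficients of variation and correlations are not touched.

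**Working it through.** **Inputs from the protocol**

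- Window: 24 h = 1,440 min after the only injection (Section 8.1; Study Summary).
- Scan start: Section 3.1 states "Emission scan will begin at the start of the radioligand infusion", so scan time is also post-injection time.
- Scan length: Section 3.1 gives the frames as "30 seconds x 6, 1 minute x 3, 2 minutes x 2, and 5 minutes x 16 for total scan time of 90 min".
- Contacts after the PET visit: none in the Section 6 text or table.

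**Input not in the protocol**

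- Stay after the end of the scan, *s*. This is an assumption, varied below.

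**Step 1: reproduce the stated scan time**

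6 × 0.5 + 3 × 1 + 2 × 2 + 16 × 5 = 3 + 3 + 4 + 80 = 90 min, which matches the plan.

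**Step 2: documented share of the window**

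Observed: 90 / 1,440 = 6.25%. Not observed: 1,350 / 1,440 = 93.75%, or 22.5 h.

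Counting from the end of the one-minute injection instead of its start moves this by 1 / 1,440, about 0.07 percentage points.

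**Step 3: allow for a stay after the scan**

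Share without scheduled contact = (1,440 − 90 − *s*) / 1,440, with *s* in minutes.

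| Assumed stay after scan | Observed (min) | Without scheduled contact |
|---|---|---|
| 0 h | 90 | 93.75% (22.5 h) |
| 0.5 h | 120 | 91.7% (22.0 h) |
| 1 h | 150 | 89.6% (21.5 h) |
| 2 h | 210 | 85.4% (20.5 h) |
| 4 h | 330 | 77.1% (18.5 h) |
| 8 h | 570 | 60.4% (14.5 h) |

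**Step 4: stay needed to cover half the window**

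(720 − 90) / 60 = 10.5 h after the scan. Section 6 describes the visits as outpatient visits, so a stay of that length is unlikely.

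**Step 5: what is collected, by time of onset**

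- *Before injection:* questioning at the PET visit can cover this.
- *Between injection and discharge:* the subject is on site. Events unresolved at discharge are followed under Sections 8.1 and 8.2.
- *Between discharge and 24 h:* no scheduled questioning. A new event is recorded only if the subject or physician believes it related and the subject reports it.

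Section 8.1 also asks for new clinically significant findings at the end of the study to be recorded, but no examination after the PET visit is scheduled at which they could be found.

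**The case against.** The strongest reply is that Section 8.1 defines a reporting period and does not promise observation. This stands. A reader might infer that the protocol claims 24 hours of active surveillance and fails to deliver it, but no section says so. A reporting window may outlast the last visit, and Section 8.2 ties questioning to any contact, not only to scheduled ones. What the reply does not explain is how the Section 8.2 duty to record all events is met once the subject has left, given that the route offered then is limited to events thought related.

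A second reply is that follow-up of existing events is already required. This also stands, and it confines the gap to events with onset after discharge.

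Third, a reader might infer that an unsupported claim of no adverse events within 24 hours is going to be published. The documents plan no such statement: safety endpoints are marked not applicable in Section 3.4, and Section 7.2 contains no safety analysis. Nor would a confidence limit on the event rate in so few subjects measure this gap; such a limit reflects the sample size and assumes complete capture.

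Fourth, a reader might infer that patients with dementia cannot report for themselves and that an informant must be called. The protocol requires patients to be able to give informed consent and to be judged likely to comply, about half the scanned subjects will be controls, and no informant is defined anywhere. Prompted questioning is still likely to capture more than unprompted report.

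Finally, the risk may be low. The ligand is given at tracer dose, and Section 1.4.1 reports no related events in over 100 subjects. That bears on the ligand more than on the arterial catheter, and it does not reconcile the sections.

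**Conclusion.** The point holds as a mismatch between the reporting period and the contacts shown. Of the 24 hours after injection, 1.5 hours (6.25%) is documented observation. Depending on the unstated stay after the scan, about 60% (8 h) to 94% (none) of the window has no scheduled contact, and more than half is uncovered for any stay shorter than 10.5 hours. The consequence is likely under-collection of adverse events that begin after discharge, above all those not thought related. It is a question of the completeness of safety data and does not affect the validity of the PET results.

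Two limits apply. The post-scan stay is assumed throughout. The consent pages were removed before review, and the schedule's column headings carry footnote markers whose text is not in the extracted document. Either could describe a follow-up contact, so it cannot be said outright that none exists, only that the Section 6 text and table show none.

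**What to change.** Reconcile Sections 8.1, 8.2 and the Section 6 schedule. Add a column for one telephone contact with each scanned subject at or just after 24 hours post-injection, with adverse events marked, and use the questioning already required by Section 8.2. Placed there, a single call brings the whole post-injection window under direct questioning. If the consent form or the schedule footnotes already provide such a contact, show it in the Section 6 table.

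The cost is about 8 short calls by existing staff (4 planned completers in each of two groups) and a minor amendment, which under Section 11 goes to the IRB. No imaging procedure or analysis changes.

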8.2 Recording of Adverse Events

At each contact with the subject, the investigator must seek information on adverse events (AEs) by specific questioning and, as appropriate, by examination. Information on all adverse events should be recorded immediately in the source document, and also in the appropriate adverse event module of the case report form (CRF). All clearly related signs, symptoms, and abnormal diagnostic procedures results should be recorded in the source document, though should be grouped under one diagnosis.

All adverse events occurring during the study period must be recorded. The clinical course of each event should be followed until resolution, stabilization, or until it has been determined that the study treatment or participation is not the cause. Serious adverse events that are still ongoing

at the end of the study period must be followed up to determine the final outcome. Any serious adverse event that occurs after the study period and is considered to be possibly related to the study treatment or study participation should be recorded and reported immediately.

As per CUMC IRB's Policy, Unanticipated Problems will be defined as follows:

Unanticipated Problem (UP) is any incident, experience or outcome involving risk to subjects or others in any human subjects research that meets all of the following criteria:

- Unexpected (in terms of nature, severity or frequency) given (a) the research procedures that are described in the IRB-approval protocol and informed consent document and (b) the characteristics of the subject population being studied;
- Related or possibly related to participation in such research (i.e., there is a reasonable possibility that the incident, experience or outcome may have been caused by the procedures involved in such research); and
- Suggests that the research places subjects or others at a greater risk of harm (including physical, psychological, economic or social harm) than was previously known or recognized (HHS IRB Guidance, Section I).

The following AEs will be considered Unexpected Problems:

- A single occurrence of a serious, unexpected event that is uncommon and strongly associated with drug exposure
- A single occurrence, or a small number of occurrences, of a serious, unexpected event that is not commonly associated with drug exposure
- Multiple occurrences of an AE that, based on an aggregate analysis, are determined not to be isolated occurrences and involve risk to human subjects
- An AE that is described or addressed in the investigator's brochure, protocol or informed consent documents (a Described AE), but occurs at a specificity or severity that is inconsistent with prior observations
- A serious Described AE, but for which the rate of occurrence represents a clinically significant increase in the expected rate of occurrence
- Any other AE or safety finding that would cause the sponsor to modify the investigator's brochure, study protocol or informed consent documents or would prompt other action by the IRB to ensure the protection of human subjects (2009 FDA Guidance, Section III (A)).

8.3 Reporting of Serious Adverse Events

8.3.1 IRB Notification by Investigator

At the time of the Occurrence of an Unanticipated Problem (UP):

Each UP will be reported to the IRB, whether or not (a) it is serious or non-serious or (b) it occurs at a site at which the PI is conducting the research.

CONFIDENTIAL

This material is the property of Columbia University Medical Center. Do not disclose or use except as authorized in writing by the study sponsor

The UP will be reported promptly, but not later than one week following the occurrence of the UP or the PI's acquiring knowledge of the UP.

The PI will make the determination as to whether an incident, experience or outcome constitutes a UP.

Each Unanticipated Problem will be reported to the IRB using the Unanticipated Problem Report module in Rascal.

The investigator must conclude in the Unanticipated Problem Report whether the protocol and/or consent form(s) should be modified as the result of the UP. If the protocol and/or consent document(s) requires a revision, a modification must be submitted in Rascal.

At the Time of Continuing Review of a Protocol:

At the time of continuing review of a protocol, the PI will submit a summary of all UPs that occurred during the review period and since the beginning of the study. The summary for each UP should include:

- The number of subjects who experienced the UP;
- The investigator's determination as to whether or not the UP was serious;
- The investigator's determination as to the UP's relationship to the study procedures (e.g., definitely related, probably related or possibly related).

